IRB	Institutional Review Board
ISO	International Organization for Standardization
LOS	Length Of Stay

Subject: smART Plus Comparative Study Protocol - Beilinson

ml	milliliter
MOP	Manual of Procedures
NCT	National Clinical Trial
NIH	National Institutes of Health
NIH IC	NIH Institute or Center
NG	Naso-Gastric
PEEP	Positive end expiratory pressure
PI	Principal Investigator
PPI	Proton Pump Inhibitors
QA	Quality Assurance
QC	Quality Control
REE	Resting Energy Expenditure
SAE	Serious Adverse Event
SAP	Statistical Analysis Plan
SOA	Schedule of Activities
SOP	Standard Operating Procedure
VAE	Ventilator Associated Event
APACHE	Acute Physiology and Chronic Health Evaluation

Subject: smART Plus Comparative Study Protocol - Beilinson

1. Protocol Synopsis

Study Title:	Nutrition Monitoring and Feeding Optimization with the smART+ System
Purpose:	To demonstrate the ability of the smART+ System to optimize the delivery of nutrition
Study Design:	Comparative, prospective, stratified randomization
Study Endpoints:	
Primary:
 
Optimization of the delivery of nutrition by the smART+ System as compared to standard of care, by automatically calculating and administering enteral feeding better than standard of care (REE or Calorimeter).
 
Secondary:
 
- Safe use of the entire system (AE/SAE directly related to any of the system components)- Decrease in ICU length of stay from admission to ICU until the decision discharge ordered- Reduction of VAE- Decrease in ventilation days- Decrease in workload related to nurse GRV time- Convenience of use of the system and the user interface (by subjective staff questionnaire)- Assessment of urine flow monitoring related to patient condition and usability
No. of Subjects:	In Beilinson site: 100 patients; 50 patients per group Approximately 200 subjects will be enrolled for the complete multi-center comparative study (100 per group)
Population:	ICU mechanically ventilated patients
Investigational Sites:	Israel, United States, Europe
Principal Investigator:	[name]
Study Duration:	Overall study duration is estimated to enroll for approximately 1 year. Enrollment rate of up to 5 simultaneous patients per site (→ 20 parallel in all 4 sites). Total participation duration: Treatment between 2 days and up to 14 days

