1.8.2. Known potential benefits

Subject: smART Plus Comparative Study Protocol - Beilinson

As explained above, the various components of the smART+ System must operate as a cohesive system in order to allow feeding optimization as demonstrated in the flowchart below. With validation of the smART+ features during the study, the clinical benefit of the device will be the lowering of risks associated with tube displacement and malpositioning as well as lowering the risks associated with reflux and aspiration.

In addition, the smART+ System is able to continuously measure the patients REE and minimize the risk of overfeeding. Therefore, by reducing overfeeding it not only achieves feeding optimization, but it also reduces the likelihood of reflux episodes due to overfeeding.

2. Objectives and Endpoints

2.1. Primary Endpoint:

 ART MEDICAL PATIENT SAFETY TECHNOLOGY	Number: CRO-C-2822	Date issued: 01-Mar-2021
	Rev.06	Page 15 of 35

Subject: smART Plus Comparative Study Protocol - Beilinson

Optimization of the delivery of nutrition by the smART+ System as compared to standard of care, by automatically calculating and administering enteral feeding better than standard of care (REE or Calorimeter).

Optimization is defined as the ability of the system to provide adequate nutrition (not overfeed or underfeed) when compared to treatment via standard of care.

Evaluation will be conducted based on an analysis and comparison of the following parameters (obtained through the hospital's electronic records for control group and smART+ records for the treated group):

- Patient caloric target set
- Volume of patient nutritional intake value versus actual patient need – this is calculated by assessing the actual nutrition delivered, discarded nutrition in the GRV bags as well as the unused quantity in discarded feed bottles (if applicable).

As part of optimization evaluation, feeding efficiency calculation ((Net nutrition delivered [ml])/ (VTBD [ml])) should be calculated for the days when the patient received enteral feeding that given under medical order, removed from the patient, or stopped feeding that was not renewed until the end of the study. Feeding efficiency should not be calculated for the days that patient has been discontinued from enteral feeding by a medical order.

2.2. Secondary Endpoints:

- Safety

Safe use of the entire system will be assessed based on the occurrence of device related AE or SAE.

- Decrease in ICU length of stay.

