3.2. End of Study Definition

A participant is considered to have completed the study if he or she has completed all phases of the study including the last scheduled procedure shown in the Schedule of Activities (SoA).

In addition, participant is considered to have completed the study if he/she is no longer required enteral feeding (due to feeding tube removal, medical order, or any other reason which feeding stopped and is not scheduled to be renewed within the 14 days of study duration).

4. Study Population

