7.2. Medical condition resulted in the decision to deliver “Comfort-oriented care”

If during the study patient's medical condition changed and the decision/preferences is NOT to receive aggressive, life-sustaining treatments but to delivered comfort-oriented care (or equivalent according to hospital policy and PI confirmation), subject should be terminated from the study.

If in this case the smART+ feeding tube cannot be removed (since a tube must be kept for drainage purposes and a new tube should not be inserted), the feeding tube can continue to be used for drainage / other treatment purposes under the comfort-oriented care.

Although in this case the smART+ feeding tube can be left inside the patient, it must be disconnected from the smART+ device (and all other smART+ components).

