7.3. Follow-Up

No follow-up will be conducted for this study. AE and SAE collection is to be conducted up until the moment the subject study participation is terminated. AEs and SAEs occurring after study termination are not to be collected or reported for the purpose of this study.

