- **Severe:** Events, sign or symptom that are intense or debilitating and that interfere with usual activities. Recovery is usually aided by therapeutic measures.

All adverse events (AEs) must have their relationship to study intervention assessed by the clinician who examines and evaluates the participant based on temporal relationship and his/her clinical judgment. The degree of certainty about causality will be graded using the categories below.

- **Probably related:** Follows a reasonable temporal sequence from study device delivery/retrieval, and cannot be reasonably explained by known characteristics of the subject's clinical data or the surgical procedure applied.
- **Possible related:** Follows a reasonable temporal sequence from study device delivery/retrieval but could have been produced by the subject's clinical state or by the surgical procedures regardless of the study device.
- **Not related:** No relationship to study device activation is perceived.

Group B- Control Group

Subject: smART Plus Comparative Study Protocol - Beilinson

AEs recorded for group B should include only related or could affect (according to PI decision) the patient's medical condition that related to urine, feeding, GRV and REE.

7.4.2.Serious Adverse Events (SAE)

SAE DEFINITION

A "serious Adverse Event is an adverse event that:

- a) led to a death,
- b) led to a serious deterioration in health that either:
 - 1) resulted in a life-threatening illness or injury, or
 - 2) resulted in a permanent impairment of a body structure or a body function, or
 - 3) required in-patient hospitalization or prolongation of existing hospitalization, or
 - 4) resulted in medical or surgical intervention to prevent life threatening illness or injury or permanent impairment to a body structure or a body function.
- c) led to fetal distress, fetal death or a congenital abnormality or birth defect.

NOTE 1: This includes device deficiencies that might have led to a serious adverse event if a) suitable action had not been taken or b) intervention had not been made or c) if circumstances had been less fortunate. These are handled under the SAE reporting system.

NOTE 2: A planned hospitalization for pre-existing condition, or a procedure required by the Clinical Investigation Plan, without a serious deterioration in health, is not considered to be a serious adverse event.

SAE REPORTING

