- The two-sample T-test or Non-parametric Wilcoxon-Mann-Whitney Rank sum test for independent samples (as is appropriate) will be applied for testing the statistical significance of the difference in the estimated nursing time that was expended for GRV activities, and the amounts of GRV removed from the patient between the study groups.
- Convenience of use of the system and the user interface scores (by subjective staff questionnaire) will be summarized in an appropriate table by study group
- The two-sample T-test or Non-parametric Wilcoxon-Mann-Whitney Rank sum test for independent samples (as is appropriate) will be applied for testing the statistical significance of the difference in the assessment of urine flow monitoring related to patient condition and usability between the study groups.
- The two-sample T-test or Non-parametric Wilcoxon-Mann-Whitney Rank sum test for independent samples (as is appropriate) will be applied for testing the statistical significance of the difference in ICU length of stay (measured from admission to ICU until the decision to discharge is ordered) between the study groups.
- Chi-square test or Fisher's Exact test (as is appropriate) will be applied for testing the statistical significance of the difference in percent of subjects experiencing Ventilation associated events between the study groups.

9.2.5 Safety:

Adverse events will be coded using the Medical Dictionary for Regulatory Activities (MedDRA, most updated version) terminology and presented in tables by System Organ Class (SOC) and Preferred Term (PT).

Subject: smART Plus Comparative Study Protocol - Beilinson

AE data will be listed individually and summarized by SOC and by PT within a system organ class for each study group.

Frequency of TEAEs (Treatment-Emergent Adverse Events) and device-related adverse events will be summarized in tables by SOC, PT and study group and by seriousness.

Chi-square test or Fisher's Exact test (as is appropriate) will be applied for testing the statistical significance of the difference in percent of subjects experienced any AE, drug-related AE and SAE between the study groups.

Concomitant medications entered into the database will be coded using the World Health Organization (WHO) Drug Reference List, which employs the Anatomical Therapeutic Chemical classification system.

10. Regulatory, Ethical, and Study Oversight Considerations

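### The safety endpoint counts only device-attributed events, and unequal event recording with no required vital status means the planned any-AE and SAE tests cannot give a valid between-arm comparison of deaths

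*Combined protocol and SAP*

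**What the plan says.** Section 2.2 defines safety by attribution: "Safe use of the entire system will be assessed based on the occurrence of device related AE or SAE". The synopsis agrees: "Safe use of the entire system (AE/SAE directly related to any of the system components". Section 5.1 makes the trial open-label, and in 7.4.1 the investigator assigns the relationship to the device.

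The analysis in 9.2.5 is wider than the endpoint. It tabulates all AEs by arm and tests the "difference in percent of subjects experienced any AE, drug-related AE and SAE between the study groups". Under 7.4.2 an adverse event is serious if, among other criteria, it "a) led to a death".

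Section 7.4.1 gives the arms different recording rules. In group A all AEs are documented, related or not, until the feeding tube is removed. In group B, "AEs recorded for group B should include only related or could affect (according to PI decision") the patient's condition in relation to urine, feeding, GRV and REE.

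Section 7.3 allows no follow-up: "AEs and SAEs occurring after study termination are not to be collected or reported for the purpose of this study". Under 7.2 a patient moved to comfort-oriented care "subject should be terminated from the study". The data lists in 5.2.8 and 5.3.5 include the times of ICU admission and discharge order, but neither vital status nor date of death. Section 3.2 counts as completed a patient who no longer needs enteral feeding for listed reasons or "any other reason which feeding stopped and is not scheduled to be renewed within the 14 days of study duration". Section 7.1 asks for a recorded reason only for discontinuation or withdrawal. No mortality analysis is specified.

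**The concern.** All-cause death is the one safety outcome that needs no judgement about cause, which matters when the person judging cause knows the allocation. The protocol expects very many AEs and SAEs in these patients (7.4.2). Attribution event by event is then fragile, and a comparison of arms carries most of the information about harm.

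That comparison needs the same events to be captured in both arms over the same period. Here one arm is captured in full and the other through a filter applied by an unblinded investigator. Deaths after comfort-oriented care drop out of both arms. If recorded deaths or SAEs were more frequent with the device, the sponsor could not tell a real excess from a recording artefact. If they were equal, that would not be reassuring either, because deaths after termination are missing.

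**Working it through.** **Inputs.** The documents give 100 per arm for the full trial, 50 per arm at this site, and two-sided testing at 5%. They give no mortality rate, no margin and no power for death, so there is no figure of the plan's own to reproduce. All mortality rates p, and the fraction f of group B deaths that get recorded, are assumptions.

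**Step 1: which deaths the text requires to be recorded.**

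| Death occurs | Group A | Group B |
|---|---|---|
| On study, any cause | Yes, as an SAE (7.4.1, 7.4.2) | Only if the investigator links it to the four named topics (7.4.1) |
| After comfort-oriented care has ended participation | No (7.2, 7.3) | No (7.2, 7.3) |
| After tube removal or other termination | No (7.3, 7.4.1) | No after termination (7.3) |

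The first row produces a bias of known direction: more recorded events in the device arm. The other rows lose deaths in both arms, and the documents do not allow the direction of any net effect to be determined.

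**Step 2: size of the artefact if recorded deaths were compared.** Suppose true mortality is p in both arms, all group A deaths are recorded and a fraction f of group B deaths is. The chance that a false device-arm excess reaches two-sided p<0.05 is

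Φ[(p − pf − 1.96·s0)/s1],

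with m = (p + pf)/2, s0 = √(2m(1−m)/n) and s1 = √([p(1−p) + pf(1−pf)]/n).

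For p = 0.20, f = 0.5, n = 100:
- expected recorded deaths are 20 against 10, and m = 0.15
- s0 = √(2×0.15×0.85/100) = 0.0505
- s1 = √((0.16+0.09)/100) = 0.0500
- (0.10 − 1.96×0.0505)/0.0500 = 0.02, so the probability is 0.51.

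| Assumed p | f = 0.75 | f = 0.50 | f = 0.25 |
|---|---|---|---|
| 10% | 9% | 27% | 59% |
| 20% | 15% | 51% | 90% |
| 30% | 22% | 72% | 99% |

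With complete recording in both arms the figure would be 2.5% in this direction. Section 9.2.5 tests SAEs as a whole and not deaths alone, so the table shows how strongly the recording rule can act. It is not a prediction of that test's result.

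**Step 3: what complete vital status would give.** The half-width of the 95% interval for the risk difference is 1.96·√(2p(1−p)/100):

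| Assumed p | 15% | 20% | 25% | 30% | 35% |
|---|---|---|---|---|---|
| Half-width (points) | 9.9 | 11.1 | 12.0 | 12.7 | 13.2 |

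At 20% control mortality, power for a true 10-point excess is 37%, and the excess detectable with 80% power is about 18 points. With this site's 50 per arm alone, the half-width at 20% is 15.7 points.

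**The case against.** A reader might infer that safety is judged solely on device-attributed events. That is true of the 2.2 endpoint but not of the plan, because 9.2.5 tests any AE and SAEs between arms. A reader might also infer that deaths in the device arm would be hidden. For on-study deaths the text points the other way: in group A they are recordable as SAEs whatever the cause, so the filter on group B inflates the device arm's relative count.

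Nor does 3.2 say that a patient who dies has completed the study. It speaks of patients who no longer need enteral feeding and does not name death. The open wording can be read to cover death, and a completer would then need no recorded reason for leaving, but a completion label would not erase an SAE already recorded.

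Absence from 5.2.8 and 5.3.5 does not prove that vital status will be missing. Those lists also omit AEs, which the Schedule of Activities collects in both arms, and the APACHE score used for stratification. Several items defer to an eCRF that is not among the documents. What stands is that the protocol does not require vital status. The group B sentence is also garbled, so how tightly it filters is uncertain, and the value of f in the working is unknown.

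These points narrow the claim without removing it. The tests in 9.2.5 depend on recording that differs by arm, and they do not isolate death.

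**Conclusion.** The concern holds in this form: the safety endpoint is limited to device-attributed events, and the wider tests in 9.2.5 cannot repair it because the arms are recorded under different rules, vital status is not required, and collection ends with participation. Mortality cannot be validly compared between arms, and the SAE comparison is biased toward more events in the device arm.

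That conclusion rests on the text alone. Its numerical size rests on assumptions: at 20% mortality, a false excess in recorded deaths would reach p<0.05 with probability 15%, 51% or 90% when 75%, 50% or 25% of group B deaths are recorded. The documents do not support saying that device-arm deaths would be concealed, or that 3.2 expressly treats death as completion.

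**What to change.** 1. Add vital status and date of death to 5.2.8 and 5.3.5. Take them from the hospital record for every randomised patient, whatever the reason participation ended, at one fixed time from randomisation. Day 14, the trial's own maximum participation, is an example. ICU discharge is a poor cut-off because the device is hypothesised to shorten ICU stay, so the observation window could differ by arm. Include randomised patients whom 7.1 treats as screen failures or replaces.
2. Amend 7.3 to permit this collection, subject to consent for patients who withdraw.
3. Apply one SAE recording rule to both arms, at least for deaths. Until that is done, do not interpret the any-AE and SAE tests in 9.2.5 as between-arm safety comparisons.
4. In 9.2.5, report all-cause deaths by randomised arm, with the risk difference and its 95% CI.
5. In 3.2, list death as its own disposition.

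The cost is a short amendment, some extra abstraction from charts already in use for ICU times, fuller SAE recording in group B, and a consent provision. No patient's treatment changes. The limitation is precision: with 100 per arm the interval is about ±10 to ±13 points at assumed mortality of 15% to 35%, so the result is descriptive and only a large excess could be shown or excluded.

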Measured from admission to ICU until the decision to discharge is ordered.

- Reduction of VAE According to the definition from the latest CDC.
- Decrease in ventilation days.

Evaluated by the number of hours of etCO2 from the hospital electronic records

- Decrease in workload related to nurse GRV time.

Patient GRV information obtained through the hospital's electronic records and the usability questionnaires, will be analyzed to determine (a) the estimated nursing time that was expended for GRV activities, and (b) the amounts of GRV removed from the patient.

- Convenience of use of the system and the user interface (by subjective staff questionnaire)

Evaluated via questionnaires filled by physician users and nurse users participating in the study.

- Assessment of urine flow monitoring related to patient condition and usability

Patient lab results obtained through the hospital's electronic records and the usability questionnaires, will be analyzed against smART+ system urine alerts, to determine if the alerts will be useful in diagnosis and usability satisfaction.

 ART MEDICAL PATIENT SAFETY TECHNOLOGY	Number: CRO-C-2822	Date issued: 01-Mar-2021
	Rev.06	Page 16 of 35
Subject: smART Plus Comparative Study Protocol - Beilinson		

3. Study Design

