4.1. Inclusion Criteria

- 4.1.1. Males and females 18 years or older
- 4.1.2. Patients that have already been admitted to ICU (admitted to the ICU for no more than 48 hours before enrollment)
- 4.1.3. Expected to be ventilated at least 48 hours after enrollments.
- 4.1.4. Patient requires enteral feeding (by naso/oro-gastric feeding tube)

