5.3.5. Data recording- group B

The following information will be acquired from the patient's medical chart (recorded in the hospital sources) for each patient:

- Initial screening: as detailed in the study eCRF
- Feeding information: Food types, amounts, rate, water delivery, parenteral nutrition, TPN, Indirect calorimeter and other nutritional data.
- Gastric residual volume: discard gastric residuals amount, GRV procedure times.
- Medications provided: as detailed in the study eCRF.
- Lab results: all patient lab results ordered during the study as well as all available lab results obtained 24 hours prior to study enrollment and added to the eCRF.
- Imaging: patient imaging (X-rays, CT, and alike) performed during the study should be obtained and added to the eCRF.
- Urine monitoring: amounts, rates, times, warnings and all data related to urinary output and diagnosis, and found in the hospital source.
- ICU submission and discharge ordering times
- Breathing data reports starting from the ICU admission (FiO2, PEEP)
- Demographics

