2.3 Length of stay:
Sample size rationale:

The rationale for sample size calculation is based on a difference in length of stay between the tested group (with smART+ System) and the current standard practice (group B).

Sample size justification:

The comparison between groups in ventilation days is reflected by Effect size.

A sample size of 100 in each group will have 90% power to detect an **effect size of 0.46** using a two group t-test with a 0.05 two-sided significance level. [1, 2]

References:

9.2 Endpoints analysis:
9.2.1 General:

All measured variables and derived parameters will be listed individually and, if appropriate, tabulated by descriptive statistics.

 ART MEDICAL PATIENT SAFETY TECHNOLOGY	Number: CRO-C-2822	Date issued: 01-Mar-2021
	Rev.06	Page 31 of 35

Subject: smART Plus Comparative Study Protocol - Beilinson

For categorical variables summary tables will be provided giving sample size, absolute and relative frequency and 95% CI (Confidence Interval) for proportions by study arm.

For continuous variables summary tables will be provided giving sample size, arithmetic mean, standard deviation, coefficient of variation (CV%), median, minimum and maximum and 95% CI (Confidence Interval) for means of variables by study arm.

All tests will be two-tailed, and a p value of 5% or less will be considered statistically significant.

The data will be analyzed using the SAS® version 9.4 (SAS Institute, Cary North Carolina).

9.2.2 Primary endpoint:

The two-sample T-test or Non-parametric Wilcoxon-Mann-Whitney Rank sum test for independent samples (as is appropriate) will be applied for testing the statistical significance of the difference in feeding efficiency between the study groups.

9.2.3 Secondary endpoints:

- The two-sample T-test or Non-parametric Wilcoxon-Mann-Whitney Rank sum test for independent samples (as is appropriate) will be applied for testing the statistical significance of the difference in number of ventilation days (Evaluated by the number of hours of etCO2 from the hospital electronic records) between the study groups.

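### ICU stay is timed from ICU admission, and ventilation hours and VAE have no start point tied to randomisation: slight noise for the two durations, and a smaller contrast for any VAE already present

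*Combined protocol and SAP*

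**What the plan says.** - **ICU stay.** Section 2.2 defines it as "Measured from admission to ICU until the decision to discharge is ordered". Section 9.2.3 repeats that start point for the test of "ICU length of stay (measured from admission to ICU until the decision to discharge is ordered) between the study groups".
- **Eligibility.** Section 4.1 admits patients "admitted to the ICU for no more than 48 hours before enrollment". Its ventilation criterion looks forward only: "Expected to be ventilated at least 48 hours after enrollments". Neither 4.1 nor the exclusions in 4.2 mention earlier ventilation or a VAE already under way.
- **Randomisation.** Section 5.1 places it after screening, in patients who are already in the ICU.
- **Ventilation days.** Sections 2.2 and 9.2.3 give the measure as "Evaluated by the number of hours of etCO2 from the hospital electronic records", with no start time.
- **VAE.** Section 2.2 gives only "Reduction of VAE According to the definition from the latest CDC". Section 9.2.3 tests the "difference in percent of subjects experiencing Ventilation associated events between the study groups", with no requirement that onset follow randomisation.
- **Data window.** Sections 5.2.8 and 5.3.5 collect FiO2 and PEEP from ICU admission in groups A and B alike.
- **Analysis.** The tests in 9.2.3 are unadjusted two-group comparisons. None takes account of time before randomisation.

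**The concern.** The device cannot change what happened before allocation. An outcome clock that opens earlier therefore carries time or events that say nothing about the device. For ICU stay this is certain, because it is the written definition. For ventilation hours and VAE the text permits it without stating it: the data window opens at ICU admission and no rule separates baseline from outcome. Two analysts working from the same records could derive different endpoints, in a trial that is open-label.

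These three outcomes are the clinical secondary endpoints sized in Section 9.1. The consequence differs by type. Randomisation balances earlier time between arms, so a duration gains variance but its mean difference stays where it was. Balance does not rescue a yes/no outcome. A patient already counted as positive cannot benefit, and equal numbers of such patients in both arms pull the two percentages together.

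**Working it through.** **1. The plan's duration figure.** Section 9.1 gives 100 per group, effect size 0.46, two-sided 0.05 and 90% power, for both ventilation days and stay. The noncentral t calculation gives 89.9% and the normal approximation 90.2%, so the figure reproduces.

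**2. Durations.** The documents give no SD, so 4 to 10 days is assumed for time after randomisation. Enrolment and randomisation are treated as simultaneous, and time before and after randomisation as independent. For the 0 to 48 h allowed by 4.1:

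- uniform spread: s_pre = 2/√12 = 0.577 day
- largest possible spread (half the patients at 0 h, half at 48 h): s_pre = 1.0 day

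The standardised effect becomes d′ = 0.46 × SD / √(SD² + s_pre²).

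| SD (days) | s_pre | d′ | Power (t-test) |
|---|---|---|---|
| 4 | 0.577 | 0.46 × 4/√16.333 = 0.455 | 89.3% |
| 10 | 0.577 | 0.46 × 10/√100.333 = 0.459 | 89.8% |
| 4 | 1.0 | 0.46 × 4/√17 = 0.446 | 88.1% |
| 10 | 1.0 | 0.46 × 10/√101 = 0.458 | 89.6% |

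A simulation of 20,000 trials at SD 5 days gave a mean difference of 2.31 days both with and without the earlier time (0.46 × 5 = 2.30). Only the variance moves. The same figures apply to ventilation hours if these are counted from ICU admission.

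**3. The plan's VAE figure.** Section 9.1 quotes an odds ratio of 2.70 at 100 per group with 90% power, and a figure of 20% that can be read as the reference rate or as the difference. Taking 20% as one arm's rate, the other has odds 0.25 × 2.70 = 0.675, so a rate of 0.675/1.675 = 40.3%. At these rates power is 88.4% without continuity correction and about 85% with it, so the stated 90% does not reproduce on this reading. That is a separate matter. The pair serves here only as an illustration consistent with the plan's odds ratio.

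**4. Effect of pre-existing events on VAE.** Let π be the share of each arm with a counted event before randomisation (assumed; the documents give none), independent of later risk. Each observed rate is p′ = π + (1 − π)p, so the risk difference is multiplied by (1 − π).

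| π | Observed rates | Difference (points) | Odds ratio | Power, uncorrected |
|---|---|---|---|---|
| 0% | 20.0% vs 40.3% | 20.3 | 2.70 | 88.4% |
| 2% | 21.6% vs 41.5% | 19.9 | 2.57 | 86.3% |
| 5% | 24.0% vs 43.3% | 19.3 | 2.42 | 82.8% |

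For the 2% row: 0.02 + 0.98 × 0.20 = 0.216 and 0.02 + 0.98 × 0.403 = 0.415.

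**The case against.** Timing stay from admission is conventional, is stated consistently, and applies to both arms under central 1:1 randomisation. For the durations the loss is a fraction of a power point in most of the range. All of this stands. Section 9.1 also does not say that 0.46 refers to time after randomisation. If it refers to stay as the plan defines it, the 90% is unaffected and what remains is a small loss of efficiency.

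The FiO2 and PEEP readings from ICU admission may be wanted as the baseline for judging VAE onset. That is a good reason to collect them, and collecting them is not the fault; what is missing is the rule that divides baseline from outcome. The external VAE definition cannot supply a window tied to this trial's randomisation. It may well make an event within 48 h of ICU admission uncommon, but the documents do not reproduce it. Section 7.4.1 treats conditions present at screening as baseline, but that text concerns group A adverse events and does not govern the VAE endpoint.

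A reader might infer something stronger: that the earlier start biases the duration comparisons, or that patients ventilated for days elsewhere before transfer cause a large loss of power. The first does not follow, because the mean difference is unchanged. The second is not supported. Ventilation hours come from the hospital's own records, no section provides for another hospital's etCO2 data, and FiO2/PEEP collection opens at ICU admission. A large loss would need a spread of prior ventilation of around 3 days across the whole sample. With 10% of patients transferred and none of the others previously ventilated, that means about 10 days each (10 × √(0.1 × 0.9) = 3.0). Nothing in the documents suggests this. Earlier ventilation on another ward of the same hospital, with etCO2 recorded, is neither mentioned nor excluded, and it cannot be sized.

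**Conclusion.** The point holds as a low-cost improvement. Pre-randomisation time is in ICU stay by definition. Pre-randomisation ventilation and VAEs are permitted in the other two endpoints because no start is stated.

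For the durations the cost is precision only: from 89.9% to about 89.3–89.8% power, or about 88% in the least favourable case at SD 4. This assumes an SD of 4 to 10 days, prior time within 48 h, and for ventilation a count that begins at ICU admission.

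VAE matters more, because there the contrast itself shrinks. At 2% to 5% pre-existing events the odds ratio falls from 2.70 to 2.57–2.42 and uncorrected power from 88% to 86–83%. Those shares and the 20% versus 40.3% pair are illustrative, and the real share may be near zero. The documents do not support a claim that the secondary comparisons are biased towards either arm or seriously underpowered for this reason.

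**What to change.** In Sections 2.2 and 9.2.3:

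- measure ICU stay from randomisation to the discharge order, and ventilation hours from randomisation, in both arms;
- count only VAEs with onset after randomisation, with the FiO2/PEEP data from ICU admission as the baseline for judging onset;
- record at screening when the current ventilation episode began, and flag any VAE already present at randomisation;
- keep admission-based ICU stay as a descriptive figure.

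The cost is a wording change, one date/time field and one flag. Section 5.1 places the randomisation algorithm inside the eCRF, so the randomisation time should be available, though the plan does not say that it is stored and this should be confirmed. The one drawback is a headline ICU stay slightly shorter than the conventional figure, which is why the latter stays in the report. Eligibility, treatment and sample size need not change.
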